These statistics, if applicable to other months in San Diego and to other geographic locations indicate that the initial job of finding qualified controls for COPD patients will be time-consuming and possibly frustrating. One final datum adds another element worth considering:

8. The San Diego case finder logged over 1,000 miles in 118 hours work during her first month on the job. Per month estimates of mileage for the remaining 5 months of the case finding period range between 400 and 750 miles per month. Arrangements should be made for re-imbusement of fuel expenses for case finders at other centers as they have been in San Diego.

The San Diego case finder lists below a series of strategies and tactics use full if other case finders encounter similar situations.

1. After obtaining the list of patients for which a matched control must be found, locate the patient's dwelling on a fairly detailed street map. Then, map out the course of the search in as much detail as the map will allow.
2. Carry a canvassing log or notebook which can be used to note information pertinent to having to possibly re-visit a portion of a neighborhood if original attempts to contact inhabitants are unsuccessful. It can also serve as a mileage log.

3. Carry the Case Finder Tally Sheet on a clip board for ease of use.
4. Before going to any neighborhood for the first time, check to find out whether a solicitor's license is required. If so, be sure to get one, and be sure the licensing bureau understands that you work for a not-for-profit organization. This will mean that IPPB will not have to pay fees for licensing.
5. Consider the possibility of using a University or Medical Center vehicle instead of your own. It may be more - or less - cost effective but its worth looking into.
6. Try to obtain a "Professional Identification Card" from the University. If you cannot obtain one in this way, have some printed identifying you with the institution and department you work for. Present this card first when you meet new folks in the neighborhoods. Showing the official License is tacky and should be used only as a last resort in convincing someone that you are who you say you are.
7. Before canvassing in any multi-family dwelling see the manager of the building first. Often, retirement complexes have rules of this nature. If you avoid making this initial contact with the complex manager, he or she may order you off the property in an embarrassing scene. License or no license.
8. If you have found a qualified and willing control, call your neuropsychological and pulmonary technicians before leaving the control's home. Establish a probable date for the control's evaluation with the techs and then tell the control. This will "seal the deal" so to speak and minimize the ambiguities for them.
9. Be aware of the laws regarding confidentiality. You cannot divulge directly or indirectly, the name of a COPD patient participating in the IPPB study even if the control knows him or her and asks only for confirmation of the fact.
10. If a selected COPD patient's neighborhood has thoroughly been canvassed without finding a qualified control, pursue the search in adjacent neighborhoods. If you're convinced that it is similar in a sociodemographic sense. If adjacent neighborhoods are not comparable call Bethesda and ask for another COPD index subject.
11. Some COPD patients may get upset if knowledge gets back to them through the neighborhood grapevine that "someone working for a Lung Disease Study" has been in the neighborhood asking questions. Consider the possibility of having your IPPB nurse call each of the COPD patients on your list to inform them of your presence and purpose before you go out into their neighborhoods.

12. Using the model provided in this package, write a letter on University or Medical Center stationery describing in detail the procedures we are asking the controls to participate in. List study contact phone numbers on it. Give the letter to persons who have qualified demographically and medically and who are willing to participate. This will provide the control with an opportunity to review what he has gotten himself into after you've gone. If he or she has questions they can use the phone to obtain answers.

V. DATA FLOW

The casefinder will be responsible for two study forms: the case finder's tally sheet; and the control screening questionnaire, examples of which are attached in their final form.

The case finders tally sheet is a form which allows the case finder to record the frequency of certain categories of response, i.e. the total number of doors knocked on, the frequency of "no answers", the frequency of "home, but unwilling to talk", the number of nondemographically matched contacts, etc.

The control screen is the instrument used for determining whether a potential control is medically qualified (healthy) to participate.

All tally sheets are sent to the appropriate neuropsychological reading center after a match has been made for a given COPD patient.

The data from both of these forms will be forwarded to Ann Arbor from the reading centers after being checked.

A note on control screens:

If in the course of administering the control screen to a prospective control, the person answers a STOP question in the positive thus disqualifying himself from participation, the case finder continues to fill out the questionnaire. This questionnaire along with those for persons who qualify is sent to the neuropsychological reading center in order that some picture be developed of the meaning of disqualification.

VI. OTHER ITEMS

- A. Trainees from each of the centers were given a demonstration of the spirometry procedures that each control would go through.
- B. Demonstrations of the neuropsychological procedures were presented to the group by the San Diego NOIT psychometrist.
- C. Role playing sessions on the conduct of control screen interviews, were held. Each trainee had the opportunity to "play" the prospective control and had several opportunities to administer the control screening questionnaire to naive "subjects".

SUMMARY

VII. SUMMARY

The case finder's training seminar covered a great deal of information. The feeling was that it (information) could not have been communicated in a more effective manner, and that, had it not been organized in such a way, the degree of uniformity and consistency required could not have been achieved.

References

The purpose of this meeting was to determine those neuropsychological and quality of life variables which would be utilized in making decisions regarding the length of the NOTT follow-up period. A complete analysis of those selected variables would be presented to a subcommittee of the Advisory Board in February and, subsequently, to the full Advisory Board in March. Such an analysis would include an assessment of treatment differences, statistical power calculations, as well as projected conclusions that would be made at the scheduled end of the NOTT study. It was decided that no more than twenty variables should be considered for this purpose.

After considerable discussion the following variables were selected:

Rennick Repeatable Battery:

(1) Percent Tests Impaired - This variable is calculated as the percent of nine tests on which a given individual is impaired. For the purposes of power calculations, a five percent difference in mean values for the 12 hour and 24 hour treatment groups would be considered clinically important.

(2) Average Impairment Rating - For the purposes of power calculations, a .10 difference in mean values for the 12 hour and 24 hour treatment groups would be considered clinically important.

NOTE: The baseline values for the above two variables will be determined from the last administration of the Rennick Repeatable Battery before randomization. If less than three administrations are available, the baseline results will be considered to be missing. Since the Rennick Repeatable Battery is administered at baseline, 1, 2, 3, and 6 months, a multivariate analysis will be utilized comparing the two treatment groups with respect to their average response at these five time points. However, attention will be focused at a comparison of the linear trend over time for the two groups. If it is necessary to reduce the number of variables for consideration, the average impairment rating may be omitted.

Halstead-Reitan Battery:

(1) Russel-Neuringer-Average Impairment Rating - For the purposes of power calculations, a .10 difference in mean values for the 12 hour and 24 hour treatment groups would be considered clinically important.

(2) Impairment Index - This index is based on eight scores. For the purposes of power calculations, a .05 difference in mean values for the 12 hour and 24 hour treatment groups would be considered clinically important.

(3) Brain Age Quotient - For the purposes of power calculations, a difference of 3 in mean values for the 12 hours and 24 hours treatment groups would be considered clinically important.

NOTE: The average change in each of the above variables between baseline and the six month anniversary will be compared for the two treatment groups.

Clinical Rating:

(1) Clinical Global Rating - For the purposes of power calculations, a .25 difference in mean values for the 12 hour and 24 hour treatment groups would be considered clinically important.

(2) Change in Global Rating - For the purposes of power calculations, a .25 difference in mean values for the 12 hour and 24 hour treatment groups would be considered clinically important.

NOTE: The average change in the clinical global rating between baseline and the six month anniversary will be compared for the two treatment groups. It will be important to indicate clearly the distinction between the above two variables.

MMPI:

(1) Number of MMPI Scores Above 70 - The MMPI scores to be considered in this count include F, HS, D, HY, PD, PA, PT, SC, SI, and MA. For the purpose of power calculations, a .50 difference in mean values for the two treatment groups would be considered clinically important.

(2) Mean Score of Ten Scales - The ten scales to be considered in the construction of this variable are listed above. For power calculations, a difference of 1 would be considered clinically important.

(3) ES (Ego Strength) Scale - For power calculations, a difference of 2.5 would be considered clinically important.

NOTE: The average change in each of the above variables between baseline and the six month anniversary will be compared for the two treatment groups. If it is necessary to reduce the number of variables for consideration, the variables labeled number of MMPI scores above 70 may be omitted.

Sickness Impact Profile:

(1) Total Score - For power calculations, a difference of 0.2 standard deviation units in mean value would be considered important.

(2) Physical Dimension - This variable will be calculated as the sum of the ambulation, mobility, and body care and movement subscales of the SIP. For power calculations, a difference of 0.2 standard deviation units in mean value would be considered important.

(3) Psychosocial Dimension - This variable will be calculated as the sum of the social interaction, communication, alternance behavior, and emotional behavior subscales of the SIP. For power calculations, a difference of 0.2 standard deviation units in mean value would be considered important.

NOTE: The average change in each of the above variables between baseline and the six month anniversary will be compared for the two treatment groups. If it is necessary to reduce the number of variables for consideration, the physical dimension and psychosocial dimension variables may be omitted.

Katz Adjustment Scale:

- (1) R1 (Social Obstreperous)
- (2) R1 (Acute Psychotism)
- (3) R1 (Withdrawal Depression)
- (4) R2
- (5) R4
- (6) Discrepancy Score

NOTE: For each of the above variables, a difference of 0.2 standard deviation units in mean value would be considered important for power calculations. The average change in each of the above variables between baseline and the six month anniversary will be compared for the two treatment groups. If it is necessary to reduce the number of variables for consideration, the discrepancy score may be omitted.

Profile of Mood States:

- (1) Total Mood Disturbance - For power calculations a difference of 0.2 standard deviation units in mean value would be considered important.

NOTE: The baseline value for this variable will be the average of the two administrations before randomization. If only one administration before randomization is available, that value will be considered the baseline value. Since the POMS is administered at baseline, 1, 2, 3, and 6 months, a multivariate analysis will be utilized comparing the two treatment groups with respect to their average response at these five time points. However, attention will be focused at a comparison of the linear trend over time for the two groups.

Home Visit Behavior Checklist:

- (1) Average of All Cluster Scores - For the purposes of power calculations, a difference of 0.2 standard deviation units in mean values for the two treatment groups would be considered important.

- (2) Average of Depression, Hostility, Anxiety, and Lethargy Scores - For the purposes of power calculations, a difference of 0.2 standard deviation units in mean values of the two treatment groups would be considered important.

NOTE: Since the home visit behavior check list is administered at months 1, 2, 3, 4, 5, and 6, a multivariate analysis will be utilized comparing the two treatment groups with repeat to this average response at these six time points. However, attention will be focused at a comparison of the linear trend over time for the two groups.

Pedometer:

The pedometer measurement was suggested as a possible variable to be considered in the comparison of the two treatment groups. However, if it is necessary to reduce the number of variables for consideration, this variable could be omitted. In fact, it was noted that this measurement, although conceptually important, is so unreliably obtained that it perhaps should be omitted anyway.

In preparing the analysis of the above variables, it was suggested that the following approaches be utilized: (1) de novo sample size calculations utilizing the standard deviations obtained from the accumulated data, (2) conditional power calculations based on data accumulated to date, (3) extrapolation of the present trend, and (4) confidence interval calculations. Moreover, in preparing the analysis, the comparability of the two treatment groups in terms of selected demographic variables should be examined.

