Besides being the most comprehensive and best validated neuropsychological test battery for diagnostic purposes, the expanded HRB is finding increasing use in predicting the problems that neurologically impaired patients have in their everyday functioning (Denerll, Rodin, Gonzalez, Schwartz and Lin, 1966; Schwartz, Denerll and Lin, 1968; [name], Chelune, and Lehman, 1977; Newnan, [name] and Lehman, 1977). Therefore, the use of this test battery will enhance the possibility of correlating changes in neuropsychological functioning with changes in quality of life in COPD patients.

In a pilot study conducted in the Neuropsychology Laboratory at the University of Colorado Medical Center, it was determined that the expanded HRB took four to six hours to administer to COPD patients. All patients tolerated the testing well, and were able to complete it in a single testing session (given periodic breaks and time out for lunch, of course).

The Repeatable Battery has been added to the study protocol in order to determine more precisely when treatment-induced neurologic changes occur. There are two main advantages to this Battery: first, it takes less than an hour to administer; and they can be re-administered at short intervals without having practice effects influence the results. Also, the sensitivity of the Repeatable Battery to drug-induced changes in CNS functioning has been demonstrated in previous research (e.g., Rennick, Keiser, Rodin, Rim and Lennox, 1974; Lewis, Rennick, Clifford, Rodin and Rim, 1976). The disadvantages of the Repeatable Battery are that it covers a restricted range of abilities (general alertness, attention,

flexibility of thinking, and motor speed and coordination) and that it is relatively new and has not yet been shown sensitive to cerebral pathology involving many etiologies. Nevertheless, used in conjunction with the expanded HRB, this battery may help determine not only the types and degrees of treatment-induced behavioral changes, but also the time it takes for such changes to occur. The following are tests included in the abbreviated Repeatable Battery (brief descriptions are provided only for tests not described in Reitan and Davison, 1974 or Wechsler, 1955):

Digit Symbol. This is abstracted from the Wechsler Adult Intelligence Scale, and has six alternate forms.

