Color Naming. This uses a test booklet containing a series of 48 sets of four colored squares which must be correctly named by the subject in sequence. Total time and errors are recorded. (See Goldstein, 1973).

Grip Strength. Grip strength with both hands is measured with the Smedley Hand Dynamometer (Lafayette Instrument Company).

Grooved Pegboard. See Reitan and Davison, 1974.

Finger Oscillation Test. See Reitan and Davison, 1974.

Trail Making Test (Part B). See Reitan and Davison, 1974. Five alternate forms of this test are available.

Sentence Writing Time. This is a test of motor speed and coordination in a familiar but complex activity. The subject is asked to write the sentence "The large dog runs fast" with the dominant hand. The sentence is presented verbally as well as visually on a 3x5 card. There are three trials, and the times from the last two trials are averaged to compute the subject's score.

Visual Search. This is a measure of elementary visual pattern matching under conditions of high visual noise. Subjects are asked to match a small checkerboard-like pattern to another one like it found in a highly redundant array of similar patterns. Eight presentations

4-2449

are made from the test booklet and total time and errors are recorded. There are two alternate forms.

Discrimination Reaction Time Test-Substitute. This replaces the original computer assisted test and provides a measure of sustained attention and discrimination speed. The subject is asked to cross out a specific number, six or nine, which appears randomly within 61 rows of 35 single digits. Each number is equally and randomly presented enabling repeated administrations with different numbers. Total time and errors are recorded.

The Repeatable Battery will be administered to each patient four times before oxygen therapy is instituted. The first three administrations constitute the training trials, and the fourth provides the baseline measures. Each patient will then be readministered the Repeatable Battery after one, two, three and six months of oxygen therapy.

Neuropsychiatric History Questionnaire. The NOTT is a study concerned with the neuropsychological concomitants of COPD and potential cognitive benefits of two forms of oxygen treatment--continuous and nocturnal.

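### The Repeatable Battery was added to show when change occurs, but its stated comparison focuses on one linear trend, which cannot date change and shrinks a sustained early effect by 32%

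*Protocol*

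**What the plan says.** **Purpose.** Protocol section I, Neuropsychological Evaluations: "The Repeatable Battery has been added to the study protocol in order to determine more precisely when treatment-induced neurologic changes occur". The same section expects the battery to show the type and degree of change, "but also the time it takes for such changes to occur".

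**Schedule.** Section I: "Each patient will then be readministered the Repeatable Battery after one, two, three and six months of oxygen therapy". The Rennick NOTE in the Minutes of NOTT Subcommittee Meeting agrees: "Since the Rennick Repeatable Battery is administered at baseline, 1, 2, 3, and 6 months". A footnote in section II treats the Lafayette and Rennick versions as essentially the same battery.

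**Analysis.** The Rennick NOTE gives two comparisons. The first is "a multivariate analysis will be utilized comparing the two treatment groups with respect to their average response at these five time points". The second receives the emphasis: "However, attention will be focused at a comparison of the linear trend over time for the two groups".

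**Important difference.** For Percent Tests Impaired it is set as a difference in means and not as a slope: "a five percent difference in mean values for the 12 hour and 24 hour treatment groups would be considered clinically important".

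**POMS.** The NOTE for the Profile of Mood States follows the same pattern: "Since the POMS is administered at baseline, 1, 2, 3, and 6 months, a multivariate analysis will be utilized", again with attention on the linear trend.

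**The concern.** A straight line assumes the same change in every month, so its slope says how much change per month and nothing about when the change began. The visits at months 1, 2 and 3 are what make timing visible, yet the emphasised summary gives them little weight.

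Two things are at stake. First, quite different time courses give nearly the same slope, so the result cannot support a statement about timing. Second, the minutes use these variables to decide how long NOTT follow-up should run. A difference that is complete by month 1 and then held would appear as a modest trend. It could be read as a small effect or as a reason to follow patients longer.

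**Working it through.** The document gives no sample size, alpha, power or standard deviation for this comparison, so there is no stated figure to reproduce.

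**Step 1. Weights, from the stated visit times only.** Times 0, 1, 2, 3, 6 have mean 12/5 = 2.4. The deviations are -2.4, -1.4, -0.4, 0.6, 3.6. Their squares are 5.76, 1.96, 0.16, 0.36, 12.96, which sum to 21.2.

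- Month 6: 12.96/21.2 = 61%.
- Baseline: 5.76/21.2 = 27%.
- Months 1-3 together: 2.48/21.2 = 12%.

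**Step 2. Expected slope by time course.** Let D be the full group difference and d(t) its value at visit t. Slope = sum[(t - 2.4) d(t)] / 21.2. The last column sets D = 5 points on Percent Tests Impaired, reading the stated five percent as percentage points.

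| Pattern of d(t) | Sum (units of D) | Slope per month | 6 x slope | With D = 5 |
|---|---|---|---|---|
| Steady build-up to D at month 6 | 21.2/6 = 3.53 | 0.167 | 1.00 | 5.0 |
| Nothing until month 6 | 3.6 | 0.170 | 1.02 | 5.1 |
| Full from month 2 | 3.8 | 0.179 | 1.08 | 5.4 |
| Full from month 3 | 4.2 | 0.198 | 1.19 | 5.9 |
| Full from month 1, maintained | 2.4 | 0.113 | 0.68 | 3.4 |
| Months 1-3 only, gone by month 6 | -1.2 | -0.057 | -0.34 | -1.7 |

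The first three rows differ by under 8%, so the slope does not separate them. The month-1 effect is attenuated by 1 - 0.68 = 32%. The transient effect changes sign.

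A 5-point difference in means also fixes no slope. It is 5 x 0.113 = 0.57 per month if complete by month 1 and 5 x 0.198 = 0.99 if it starts at month 3. A power calculation for the trend therefore needs a time course that the NOTE does not give.

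**Step 3. Power for the month-1 maintained effect.** Assumptions that are not in the documents: two-sided alpha 0.05, equal variances, and a common between-visit correlation rho of 0.5, 0.7 or 0.8. The sample size is set so that the baseline-adjusted month-6 difference has 80% power (drift 2.80).

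- *Slope.* Drift = 2.80 x 0.1132 x sqrt[21.2(1 + rho)] = 1.79, 1.90, 1.96. Power is 43%, 48%, 50%.
- *Test of the four baseline-adjusted visit differences (4 df).* Noncentrality = 7.85 x 4(1 + rho)/(1 + 4 rho) = 15.7, 14.0, 13.5. Power is 91%, 87%, 85%.

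**Step 4. A different scaling.** Size the trial instead so that the slope has 80% power for a steady build-up, and allow AR(1) correlation (0.7 or 0.9 per month) as well as a common correlation (0.5 or 0.7). For the month-1 maintained effect the slope then has about 48% power in all four cases. An unadjusted 4-df test of the change profile has 75% under the common correlation and 99-100% under AR(1). For the steady build-up itself, that 4-df test has only about 60%, so the trend keeps a use.

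**The case against.** **The NOTE serves another purpose.** The minutes were written to choose variables for the decision on follow-up length, and their closing paragraph asks for conditional power and an extrapolation of the present trend. A trend comparison suits that decision, and nothing in the minutes bars a visit-by-visit analysis elsewhere. This stands as a reason to keep the trend. It does not remove the mismatch: the only comparison emphasised for this battery cannot address the reason given for including it.

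**The plan as a whole would miss a full early effect.** A reader might infer this from the slope's power. The documents do not support it. The multivariate comparison in the same NOTE, if it tests the vector of visit means, keeps about 85-91% power in step 3. The slope itself is attenuated and not lost, because baseline is among its five points. Two limits remain. A significant global test does not say when change occurred. And the phrase about average response could mean one average over all five visits, which would include baseline, dilute a month-1 effect to 4/5 of D and carry no timing information.

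**The POMS is equally affected.** A reader might infer this from the matching NOTE. The timing purpose is stated for the Repeatable Battery only. For the POMS, section I says that it is brief and is therefore used repeatedly. Only the loss of sensitivity to an early effect carries over.

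**The IPPB comparison is affected.** It is not. Section II.B gives this battery at baseline and twelve months only, so neither a trend nor an onset can be estimated there. The 12-hour against 24-hour comparison is NOTT's.

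**Conclusion.** The point holds as a mismatch between a stated aim and the comparison given the focus. The aim is to find when change occurs. The focus is one slope in which months 1-3 carry 12% of the weight, and for which onset at month 2, onset at month 6 and a steady build-up agree within 8%. A sustained month-1 effect is attenuated by 32%, and an effect gone by month 6 gives a slope of the opposite sign. These figures rest only on the stated visit times.

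The power figures (43-50% for the slope, about 85-91% for a test of the visit means) rest on the assumed alpha, equal variances and common correlation. They show that the choice of focus matters. They do not show that the plan would fail to detect an early effect. Neither comparison, as worded, dates the change. The conclusion is limited to the Rennick NOTE in the NOTT minutes, with a weaker, sensitivity-only case for the POMS NOTE. It is an improvement to make at no data cost.

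**What to change.** In the Rennick NOTE:

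1. State that the multivariate comparison is of the vector of visit means, with time as a categorical factor.
2. Report the baseline-adjusted group difference with its confidence interval at months 1, 2, 3 and 6, beside the linear trend, and read timing from these estimates.
3. Keep the linear trend for the follow-up-length decision.

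Do not define onset as the earliest significant month, and do not test the months in the fixed order 6, 3, 2, 1. Under the assumptions of step 3, that sequence stops at month 6 in about 95% of cases when the effect is present at months 1-3 and gone by month 6. It names month 1 as onset in only 51-54% of cases when the effect is complete by month 1 and maintained. Non-significance at a visit is not absence of effect.

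The same reporting can be added to the POMS NOTE, justified by sensitivity alone. Nothing changes in the IPPB schedule.

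The cost is wording and a few more reported estimates, with no new visits or data. Single-visit intervals will be wider than a pooled summary, so timing should be described as an estimate with its uncertainty and not as a fixed date.
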